6.2.2. Optional Extended Use Treatment Period

Directions for preparation and administration of IMP to the participant in-clinic are provided in the Pharmacy Manual for the optional EUT period. Directions for preparation and administration of IMP for home use will be provided to the participants.

Only participants enrolled in the study may receive IMP, and only authorized study personnel may supply IMP. All IMP must be stored according to the labeled instructions with access restricted to necessary clinic personnel. The site will be required to keep a temperature log to establish a record of compliance with storage conditions. Refer to the Pharmacy Manual for the optional EUT period for shelf-life and storage conditions.

The Investigator, institution, or the head of the medical institution (where applicable) is responsible for IMP and dosing devices accountability, reconciliation, and record maintenance (e.g., receipt, reconciliation, and final disposition records). Directions for storage, handling, accountability, and destruction are provided in the Pharmacy Manual for the optional EUT.

6.3. Measures to Minimize Bias: Randomization and Blinding

Not applicable.

6.4. Study Intervention Compliance

6.4.1. Inpatient Treatment Period (Single Dose)

Study participants will receive the TPIP dose directly from the Investigator or designee, under medical supervision, in an appropriate inpatient setting. The date and time of the dose administered will be recorded in the source documents. The dose of TPIP and study participant identification will be confirmed at the time of dosing by a member of the study site staff other than the person administering the TPIP.

6.4.2. Optional Extended Use Treatment Period

At each in-clinic visit, participants will be dispensed adequate IMP to allow for daily dosing. When participants are dosed at the site, IMP administration will be overseen by study site personnel. The date and time of each dose self-administered in the clinic will be recorded in the source documents. The dose of IMP and study participant identification will be confirmed at the time of dosing by a member of the study site personnel.

When participants administer IMP at home, compliance with IMP will be assessed at each in-clinic visit. Participants will record their daily dose on paper dosing diaries. Compliance will be assessed by direct questioning, review of participant dosing diaries, and counting of returned capsules during the site visits. Participants will return unused capsules and used study capsules and devices to the study site at each in-clinic visit. Participants who undergo a study drug taper will return unused capsules and used capsules and devices to the study site at a follow-up visit. Unused capsules should be returned in the bottle they were dispensed in. Deviation(s) from the prescribed dosage regimen should be recorded.

A record of the quantity of capsules dispensed to and administered by each participant must be maintained and reconciled with study drug logs and participant dosing diaries. Study drug start and stop dates, including dates for study drug interruptions and/or dose reductions will also be recorded.

6.5. Dose Modification

Dose modification is part of the study design and is described in detail in [Section 4.3](#) and [Section 1.3.2](#).

6.6. Continued Access to Study Intervention After the End of the Study

Not applicable.

6.7. Treatment of Overdose

An overdose is defined as the participant receiving any TPIP in excess of their assigned dose as predetermined by the SRC ([Section 4.3](#)). An overdose itself is not an AE. However, if the overdose results in clinical signs and symptoms, it requires expedited reporting as if it is an SAE. The Investigators must refer to the relevant documents for detailed information regarding warnings, precautions, contraindications, AEs, and other significant data pertaining to the study IMP. Such documents may include, but are not limited to, the Investigator's brochure.

In the event of an overdose, the Investigator must:

- Contact the Medical Monitor within 24 hours.
- Evaluate the participant to determine, in consultation with the Medical Monitor, how to proceed with treatment period procedures and assessments.
- Closely monitor the participant for any AE/SAE and laboratory abnormalities until TP or TRE is likely to be sufficiently metabolized and/or excreted and/or can no longer be detected systemically. The frequency and duration of plasma sampling from the last dose of TPIP must be determined by the Investigator in conjunction with the study team and Medical Monitor.
- The overdose must be fully documented (e.g., quantity of the excess dose, duration of the overdose, how it happened) in the CRF.

6.8. Concomitant Therapy

Any medications, treatments, or therapies that the participant is receiving at Baseline (Study Day 1) or receives during the study (Study Day 1 through end of study [EOS]) are considered concomitant therapy and will be collected and documented in the study CRF.

Documentation includes the name of the therapy, with the reason for use, the dates of administration including start and end dates, and dosage information including dose and frequency.

Prior medications are those medications taken before the first dose of study IMP. A medication that starts prior to first dose but continues after the first dose of study IMP is classified both in prior and concomitant medications. Any procedures performed from Day 1 through EOS are considered concomitant procedures and will be collected and documented in the study CRF.

The Medical Monitor must be contacted if there are any questions regarding concomitant or prior therapy.

For participants who enroll in the EUT period, new concomitant therapy for the period from the single-dose Study Day 30 follow-up until the enrollment in the EUT will be collected during participant's screening for the EUT.

6.8.1. CYP2C8 Inhibitors

Use of CYP2C8 inhibitors may increase the systemic exposure to TRE and should be avoided prior to initiation of study drug administration. Should the use of any of these medications within the specified pre-Baseline window or during the study be considered essential, the Investigator should consult the study Medical Monitor prior to dosing.

Table 7: Windows for CYP2C8 Inhibitor Medications

Medication	Minimal Time from Last Dose to Baseline
Gemfibrozil	1 day
Trimethoprim	1 week
Montelukast	3 days
Clopidogrel	3 days

7. DISCONTINUATION OF STUDY IMP AND PARTICIPANT DISCONTINUATION/WITHDRAWAL

7.1. Discontinuation of Study IMP

7.1.1. Single-dose Period

This is a single dose period; not applicable.

7.1.2. Optional Extended Use Treatment Period

If study drug is permanently discontinued, the participant will be encouraged to participate in their remaining study visits. See [Table 6](#) for data to be collected at the time of discontinuation of IMP and follow-up. If a participant discontinues the study and needs to be started on another PAH medication, the Investigator should contact the Medical Monitor.

7.2. Participant Discontinuation/Withdrawal from the Study

A participant may withdraw from the study at any time at his/her own request or may be withdrawn at any time at the discretion of the Investigator for safety, behavioral, or compliance reasons.

At the time of discontinuing from the study after study drug administration, if possible, an early discontinuation evaluation should be conducted to maximize participant safety. This final evaluation and the reason for participant withdrawal must be documented in the CRF.

The participant will be permanently discontinued both from the study drug and from the study at that time.

If the participant is discontinued from the study due to an SAE, the Investigator will follow the participant until the Investigator deems that the SAE has resolved or stabilized.

The Investigator may withdraw the participant from the study due to absence of a PD response to TPIP. Lack of expected pharmacological action per se will not be reported as an AE or SAE. Such instances will be captured in the PK and PD assessments.

If the participant withdraws consent for disclosure of future information, Insmed may retain and continue to use any data collected before such a withdrawal of consent.

If a participant withdraws from the study, he/she may request destruction of any samples taken and not tested, and the Investigator must document this in the site study records.

7.3. Lost to Follow Up

A participant will be considered lost to follow-up if he or she repeatedly fails to return for scheduled follow-up visits and is unable to be contacted by the study site.

The following actions must be taken if a participant fails to return to the clinic for a required study visit:

- The site must attempt to contact the participant and reschedule the missed visit as soon as possible and counsel the participant on the importance of

maintaining the assigned visit schedule and ascertain whether or not the participant wishes to continue in the study.

- Before a participant is deemed lost to follow up, the Investigator or designee must make every effort to regain contact with the participant (where possible, 3 telephone calls and, if necessary, a certified letter to the participant's last known mailing address or local equivalent methods). These contact attempts must be documented in the participant's medical record.
- Should the participant continue to be unreachable, he/she will be considered lost to follow-up and to have withdrawn from the study.
- Site personnel, or an independent third party, will attempt to collect the vital status of the participant within legal and ethical boundaries for all participants, including those who did not get study IMP. Public sources may be searched for vital status information. If vital status is determined as deceased, this will be documented and the participant will not be considered lost to follow-up. Insmed personnel will not be involved in any attempts to collect vital status information.

Discontinuation of specific sites or of the study as a whole are handled as part of Appendix 1 ([Section 10.1.13.2](#)).

8. STUDY ASSESSMENTS AND PROCEDURES

Study procedures and their timing are summarized in [Table 1](#), [Table 2](#), [Table 3](#), [Table 4](#), [Table 5](#), and [Table 6](#).

All screening evaluations must be completed and reviewed to confirm that potential participants meet eligibility criteria prior to scheduling the study RHC procedure and inpatient admission. The RHC procedure and inpatient admission must be scheduled for as soon as possible once the participant's eligibility for the study is confirmed by screening. The Investigator will maintain a screening log to record details of all participants screened and to confirm eligibility or record reasons for screening failure, as applicable.

Procedures conducted as part of the participant's routine clinical management (e.g., previous RHC, previous echocardiogram, previous 6MWD test) and obtained before signing of the ICF may be utilized for screening or Baseline purposes provided the procedures meet the protocol-specified criteria and were performed within the time frames defined either in the inclusion and exclusion criteria in Section 5 or in the SoA (Section 1.4).

For participants who do not elect to enter the EUT period, the maximum amount of blood collected from each participant over the duration of the study, including any extra assessments that may be required is expected to be approximately 140 mL and will not exceed 200 mL. Approximately 80 mL will be required for PK sampling over 48 hours and approximately 20 mL for biomarker sampling. Safety and screening blood samples will require approximately 20 to 30 mL. Blood loss from the RHC procedure is anticipated to be negligible.

For participants who do elect to enter the optional EUT period within the 30 day follow-up window in the single-dose period, there is no anticipated blood collection. For participants who elect to enter the optional EUT period after the 30 day follow-up in the single-dose period, Safety and screening blood samples will require approximately 20 to 30 mL. Blood loss from the RHC procedures is anticipated to be negligible.

Repeat or unscheduled samples may be taken for safety reasons or for technical issues with the samples at the Investigator's discretion.

At any time, the Investigator has the option to discontinue assessments for participant safety or tolerability reasons. Additional laboratory, PK, and/or hemodynamic assessments may be performed as deemed necessary for participant safety. Following completion of scheduled events, the Investigator has the option of continued laboratory and/or hemodynamic monitoring as deemed appropriate for participant safety. If, in the interest of participant safety, the Investigator omits scheduled assessments/procedures or performs additional assessments/procedures, the reason for doing so must be reported on the CRF as an AE in order to avoid a protocol violation.

8.1. Pharmacodynamic Assessments

The results of each individual participant's PD assessments will contribute to the dosing decision for the next participant ([Section 4.3](#)).

8.1.1. Required PD Assessments with RHC

PVR, CO, PAP (mean), RAP (mean), RVP, hemoglobin, and MVO₂ will be measured via the RHC at the time points indicated in the SoA ([Table 2](#)). Oxygen consumption is part of the MVO₂ calculation and may be measured or estimated at 125 mL O₂ per square meter (m²) of body surface area (BSA). These or other parameters may be optionally measured at other time points or omitted to ensure participant safety at the Investigator's discretion. If measurements are missed, or additional measurements are taken for safety purposes, the reason must be documented as an AE in the CRF.

Institutional procedures for insertion, care, monitoring, and removal of the RHC will be followed. Specific technique and procedures for measurement of PVR, CO, PAP, RAP, RVP, hemoglobin, oxygen consumption, and MVO₂ are provided in a separate Procedure Guide.

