1.3.2.1. Inpatient Treatment Period Dose Selection

Each participant will enter the study in a serial fashion, following review of available safety, PK, and PD data from all previous participants by the Safety Review Committee (SRC). Each participant will receive a single-dose administration of TPIP via a dry powder inhaler. TPIP will be administered to only one participant at a time, with full evaluation of all available data prior to dosing the next participant.

The first participant will receive a dose of TPIP containing 112.5 µg. Subsequent participants will receive 80 µg, or a combination of capsules containing 80 µg, 160 µg, and 320 µg of TP,

based on SRC recommendations. After the first participant, the SRC will review all available safety, PD, and PK data including data from the first participant and select the TPIP dose and any changes to the assessments for the second participant. Then, following review of all available data including that from the first and second participants, the SRC will select the dose for the third participant. Similarly, all available data from previous studies and participants will be assessed prior to determining the dose for the next participant, until such a time as the SRC believes the study must conclude. [Figure 3](#) describes the planned dose-selection and study continuation process.

Figure 3: Schematic of Study Continuation Planning after Participant 1, INS1009-201

SRC=Safety Review Committee

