1.4. Schedule of Activities (SoA)

The SoA is divided into the following tables:

- Screening and follow-up activities in the single-dose period
- SoA in the inpatient treatment period

- PK and PD biomarker blood sampling schedule
- Optional procedures and assessments in the inpatient treatment period
- Screening and follow-up activities in the EUT period
- SoA in the EUT period

The single-dose period refers to the combination of the inpatient treatment period (Study Day 1 to Study Day 2), the PK/PD sampling period, and the 30 day follow-up period.

Table 1: Schedule of Activities for Screening and Follow up, Single-Dose Period, INS1009-201

Procedure	Screening	Follow-up	
	Up to 30 Days	48 h post TPIP dose ^a	Study Day 30 (± 2 days) ^b
Informed Consent	X	--	--
Inclusion/Exclusion Criteria	X	--	--
Demographics and Medical History	X	--	--
Smoking Status	X	--	--
Height, Weight	X	--	--
Prior/Concomitant Medications	X	X	X
Serology (HBsAg, HIV antibody, HCV antibody)	X	--	--
Serum Pregnancy Test (WOCBP only)	X	—	—
Urine Pregnancy Test (WOCBP only)	--	—	X
Hematology, Clinical Chemistry (Table 8)	X	X	--
Coagulation Profile (Table 8)	X	--	--
12-lead ECG	X	X	--
Physical Examination	X	X	--
Vital Signs	X	X	--
Pulmonary Function Testing (if needed, (Section 5.1)	X	--	--
Adverse Events ^c	X	X	X

^a 48 h safety follow-up assessments are to be conducted at the time of the visit for the 48h PK blood draw ([Table 3](#)).

^b Follow-up visit will be shortened and conducted just prior to administration of IMP in the extended treatment period if the visit overlaps with the start of the extended treatment period.

^c AE collection is from the time of signing the informed consent through the Day 30 safety follow-up. Events between ICF signing and TPIP dosing that are serious will be recorded as SAE; non-serious events during this period must be recorded as medical history.

BMI = body mass index; ECG = electrocardiogram WOCBP = woman of childbearing potential

Note: Additional safety follow-ups may be conducted at any time per the investigator's discretion to ensure participant safety. The reason for any additional safety follow-up must be reported as an AE.

Table 2: Schedule of Activities for Inpatient Treatment Period, INS1009-201

	Treatment Period (Study Day 1 to Study Day 2)													
	Pre-TPIP Administration			TPIP Administration	Post-TPIP Administration									

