3. OBJECTIVES AND ENDPOINTS

Objectives	Endpoints
Primary	Primary

 To evaluate the safety and tolerability of single doses of TPIP in participants with PAH 	
 Frequency of TEAEs
Secondary	Secondary

 To evaluate the effects of single doses of TPIP on PVR in participants with PAH over the first 24 hours following administration To evaluate the PK of TRE in participants with PAH 	
 Change from Baseline in PVR at 8 and 24 hours after TPIP administration C_{max}, t_{max}, AUC_{t1-t2}, $AUC_{0-\infty}$, $t_{1/2}$ of TRE in plasma
Exploratory	Exploratory

 To evaluate the PD effects of single doses of TPIP in participants with PAH over 24 hours following administration To evaluate the PD effects of NO challenge in participants with PAH over 24 hours following administration To evaluate the effect of single doses of TPIP on selected biomarkers in participants with PAH over 24 hours following administration 	
 Change from Baseline in PVR, PAP, RVP, RAP, CO, oxygen consumption, MVO_2, SpO_2, heart rate, systemic blood pressure, hemoglobin, at selected time points after TPIP administration Change from Baseline in PVR, PAP, RVP, RAP, CO, oxygen consumption, MVO_2, SpO_2, heart rate, systemic blood pressure, hemoglobin, at selected time points after NO challenge Change from Baseline in selected biomarker concentrations at selected time points after TPIP administration

 To evaluate changes in clinical laboratory parameters in participants with PAH after TPIP administration 	
 Clinically relevant change from Baseline in hematology, coagulation, and clinical chemistry parameters (Section 10.2, Table 8)

 To evaluate the PK of TP in participants with PAH To evaluate the PK of TRE in participants with PAH 	
 Plasma PK parameters of TP, such as C_{max}, t_{max}, AUC_{t1-t2}, $AUC_{0-\infty}$, $t_{1/2}$, CL/F and Vd/F Plasma PK parameters of TRE, such as C_{max}, t_{max}, AUC_{t1-t2}, $AUC_{0-\infty}$, $t_{1/2}$, CL/F and Vd/F

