10.1.7. Committee Structure

An SRC will be responsible for monitoring safety data. The SRC will comprise all Investigators and key members of the Insmed Study Team (including but not limited to Medical Monitor, Medical Director(s), Safety/Pharmacovigilance Physician, Statistician, Clinical Pharmacologist) and external expert consultants. The SRC will continuously monitor all available safety, PD and PK data for each participant and will obtain consensus regarding the safety of continuing the study, the next TPIP dose, and clinical care of the next participant. Expert consultants may be invited to review and interpret participant data. With any safety findings, a decision will be made, based on the review, as to whether enrollment in the study will be allowed to continue. Decisions regarding final database values for PD parameters may be adjudicated by the SRC.

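### Oxygen consumption may be a fixed estimate while its change from Baseline is an endpoint: the change is zero by construction, or spurious if the method differs between times

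*Protocol*

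**What the plan says.** Protocol Section 8.1.1 names the parameters taken through the right heart catheter ("PVR, CO, PAP (mean), RAP (mean), RVP, hemoglobin, and" MVO2). It then ties oxygen consumption to the MVO2 "calculation and may be measured or estimated at 125 mL" of O2 per m² of body surface area (BSA). It sets no rule on which option applies when, and none on keeping one option within a participant. The same section adds: "Specific technique and procedures for measurement of PVR, CO, PAP, RAP, RVP, hemoglobin, oxygen consumption, and" MVO2 are in a separate Procedure Guide, which is not at hand.

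Section 3 lists as an exploratory endpoint "Change from Baseline in PVR, PAP, RVP, RAP, CO, oxygen consumption" and further variables, once for times after TPIP and once for times after NO challenge. The secondary PD endpoint is "Change from Baseline in PVR at 8 and 24 hours after TPIP administration".

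The abbreviation list and the footnotes to Table 2 define MVO2 as mixed venous oxygen saturation. In Section 1.4, Table 1 schedules "Height, Weight" at Screening only for the single-dose period.

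On the handling of PD values, Section 10.1.7 says: "Decisions regarding final database values for PD parameters may be adjudicated by the SRC".

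**The concern.** A change-from-Baseline endpoint needs a quantity that can change. A value set at a constant times BSA cannot change between Baseline and 24 hours, because BSA is fixed over that time. A participant estimated throughout would contribute a zero that reads as no effect but carries no information. A participant measured at one time and estimated at another would contribute a difference between methods.

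Either case is foreseeable. The only gas-exchange assessment in the protocol (Section 8.1.4, Table 4) is optional. It lists carbon dioxide production but not oxygen consumption, and it omits the 12-hour time at which catheter measurements are taken.

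The sentence is also wrong on its face. Mixed venous saturation is read from blood drawn through the catheter, and oxygen consumption is not an input to it. Oxygen consumption is an input to cardiac output (CO) when the Fick method is used. As written, the sentence hides whether the choice between measuring and estimating reaches CO and PVR at all.

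What is at stake is the exploratory oxygen-consumption endpoint and, under one condition, the secondary PVR endpoint. Results are to be shown individually for about 6 to 10 participants with no control arm, so neither averaging nor a comparator would remove an artefact. Section 8.1 also says PD results contribute to the next participant's dosing decision.

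**Working it through.** The plan gives no derived figure to reproduce; its only number here is 125 mL per m², read as per minute.

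**Inputs.** From the protocol: the 125 mL figure, and height and weight at Screening only. Assumed for illustration: BSA 1.5 to 2.1 m², and true resting consumption 100 to 150 mL/min/m² (125 ± 20%).

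**1. Estimated at both times.** VO2 = 125 × BSA.
- BSA 1.5: 187.5 mL/min before and after
- BSA 1.8: 225.0 mL/min before and after
- BSA 2.1: 262.5 mL/min before and after

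The change is 0 in every case, for any true effect.

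**2. Method differs, nothing truly changes.** Let m be the measured value per m².
- Measured at Baseline, estimated after dose: change = 125/m − 1. For m = 100 this is +25%; for m = 150 it is −16.7%. At BSA 1.8 that is (125 − 100) × 1.8 = +45 mL/min and (125 − 150) × 1.8 = −45 mL/min.
- Estimated at Baseline, measured after dose: change = m/125 − 1, which is −20% to +20%.

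**3. PVR, only if CO is by Fick (an assumption).** CO = VO2 / (13.6 × Hb × (SaO2 − SvO2)) and PVR = (mPAP − PCWP)/CO. For given pressures, haemoglobin and saturations, calculated PVR is therefore proportional to 1/VO2.
- Measured at Baseline, estimated after dose, no true change: PVR ratio = m/125, a false change of −20% to +20%.
- Estimated at Baseline, measured after dose: ratio = 125/m, a false change of +25% to −17%.
- Estimated throughout, true consumption falls 10%, true CO and pressures unchanged: the arteriovenous difference falls 10%, and calculated PVR falls 10%. With assumed Hb 13.5 g/dL, saturations 95% and 65%, pressure gradient 30 mmHg and BSA 1.8, CO is 225/(13.6 × 13.5 × 0.30) = 4.08 L/min and PVR is 30/4.08 = 7.34 WU. With the difference at 0.27, calculated PVR is 7.34 × 0.9 = 6.61 WU.
- Estimated throughout, true consumption constant but not 125: percent PVR change is unaffected, and absolute change is multiplied by m/125, that is 0.8 to 1.2.

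**4. PVR, if CO does not use oxygen consumption (for example thermodilution).** The error from this source is 0%.

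**The case against.** The strongest reply is that measurement technique, including CO and oxygen consumption, belongs to the Procedure Guide, which may fix the CO method and require consistency within a participant. That stands as far as CO and PVR go: silence in the protocol does not show that sites are free to switch. It does not rescue the oxygen-consumption endpoint. A guide that imposed estimation consistently would still yield zero change, because the protocol itself permits a constant.

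A second reply concerns weight. Oxygen consumption is exploratory, PVR is secondary, the primary endpoint is the frequency of treatment-emergent adverse events, there is no hypothesis testing, and PK and PD data are listed and graphed by participant. That also stands, and it limits the importance of the point. A constant would be visible in a listing. A switch of method would be harder to see without a field that records it.

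Three stronger readings are tempting, and the documents do not support them.
- A reader might infer that PVR change is an artefact of assumed oxygen consumption. Joint collection of haemoglobin, SpO2, MVO2 and oxygen consumption is compatible with Fick but does not establish it. The protocol also gives no expected PVR effect against which to judge such an error.
- A reader might infer that the SRC will alter PVR values to suit the dose. The committee does choose doses ("the SRC will select the dose for the third participant"), and the protocol sets no adjudication criteria or masking. But the text speaks of adjudication, membership includes external consultants, criteria may sit in a document not shown, and Section 10.1.9.1 provides an audit trail of every modification. This is a possible route for bias, not a shown error.
- A reader might infer from the list in Section 8.1.1 that PCWP is missing, so that post-dose PVR cannot be calculated. Table 2 schedules PCWP at every catheter assessment.

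**Conclusion.** The point holds for oxygen consumption. Wherever it is estimated at both times, its change from Baseline is exactly zero by construction; this needs no assumption beyond a fixed BSA, which the single-dose schedule implies. Where Baseline is measured and the later value estimated, a spurious change of about +25% to −17% can appear. That range rests on assumed true values of 100 to 150 mL/min/m², which are not in the protocol.

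The statement that oxygen consumption is part of calculating MVO2 contradicts the protocol's own definition of MVO2 as a saturation measured through the catheter.

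Distortion of PVR change is conditional on Fick CO. Under that condition it can reach the sizes shown for a switched method or a shift in true consumption; otherwise it is zero. On SRC adjudication, all that is supported is that site-recorded values should be visible beside adjudicated ones.

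**What to change.** - Reword the MVO2 sentence in Section 8.1.1 so that it agrees with the CO method in the Procedure Guide. It should not simply be changed to Fick, since that could contradict the guide.
- Record on the CRF whether oxygen consumption was measured or estimated, and how CO was obtained.
- Use one method per participant at Baseline, post-NO Baseline and all post-dose times.
- Report change in oxygen consumption, after TPIP and after NO challenge, only where it was measured at both times.
- Where the SRC adjudicates a PD value, list the site-recorded value beside the adjudicated one, with the reason.

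The cost is wording, CRF fields for the methods and for adjudication, and fewer participants contributing to the oxygen-consumption endpoint. Those lost would have contributed zeros or method differences rather than information.
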